2.3. Exploratory Objective

The exploratory objectives of this study are:

- 1. Evaluate tissue immune responses to VGX-3100 in cervical samples
- 2. Describe association of microRNA (miRNA) profile, DNA methylation profile, previous colposcopy, cytology and HPV testing results with Week 36 histologic regression
- 3. Describe the durability of virologic clearance of HPV-16 and/or HPV-18 for subjects treated with VGX-3100 compared with those treated with placebo
- 4. Describe the patient-reported outcomes (PRO) for subjects treated with VGX-3100
- 5. Determine whether a tissue-based score derived using an immunologic markers (Immunoscore) at baseline is predictive for histological and virological response to VGX-3100 at Week 36

3. Investigational Plan

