3.2.3. Exploratory Endpoints

The exploratory endpoints of this study are:

- 1. Assessment of markers including but not limited to CD8+ and FoxP3+ infiltrating cells. Additional assessments may include visualization of Granulysin, Perforin, CD137, CD103 and PD-L1 in cervical tissue as sample allows. Markers listed here may change as new relevant information becomes available
- 2. Colposcopy, cytology, and HPV test results (Weeks 8, 15 and 28 visits), miRNA profile (baseline, Week 8) and DNA methylation profile (baseline, Week 15) in conjunction with histologic regression of cervical HSIL at Week 36 visit
- 3. Proportion of subjects with no evidence of HPV-16 and/or HPV-18 by type specific HPV testing at Weeks 62 and 88 visits
- 4. Patient-reported outcome questionnaires self-administered at baseline, after each dose at Weeks 4, 12, 8-14 days following each dose, and at Weeks 28, 36, 40 and 88 by subjects enrolled in US, Canada, Mexico, Germany and UK
- 5. Immunoscore results for VGX-3100 treated subjects and in conjunction with histological and virological outcomes at Week 36

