7.2. Study Treatments

Number of doses taken and percentage of subjects at number of doses will be summarized by the treatment arm.

8. Efficacy Analysis

All of the efficacy endpoints analyses will use the ITT population. Analyses of primary and secondary efficacy endpoints with the mITT and PP populations will be considered supportive of the corresponding ITT population.

Subgroup analysis of the primary and secondary efficacy endpoints will also be conducted by history of exposure to prophylactic HPV vaccines.

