Subject with no histologic evidence of cervical HSIL ^a at Week 36 evaluation and no evidence of HPV-16 and/or HPV-18 at Week 36 ^b AND Subject in which an excision or biopsy sample ^c was NOT obtained between initial dose up to Week 36	OR Subject with evidence of HPV-16 or HPV-18 at Week 36 OR Subject in which an excision or biopsy sample was obtained between initial dose up to Week 36 OR Subjects with no Week 36 sample result

a. No evidence of HSIL is defined by histology as negative, squamous atypia, or LSIL

c. Excludes ECC-only samples

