8.4. Exploratory Analysis

The relationship between the histologic regression of cervical HSIL with virologic clearance at Week 36 visit (Y/N) and a) miRNA results, b) DNA methylation results, c) colposcopy results, d) cytology results, e) HPV results, and f) baseline immunoscore results (tissue-based score derived using immunologic markers) will be examined using separate logistic regression models for each result, with histologic regression of cervical HSIL with virologic clearance as the response variable, and each of the results and treatment arm as regressor variables. Odds Ratios (ORs) and corresponding 95% CIs will be provided for the regressor variables.

Durability, as measured by clearance of HPV-16 and/or HPV-18 infection at Week 62 and 88, will be summarized by number and percentage of subjects with no evidence of HPV-16 and/or HPV-18 by treatment arm at each visit. Specifically, the virology results at Week 62 are those between Day 420 and Day 448, and the virology results at Week 88 are those between Day 602 and Day 630.

Assessment of markers including but not limited to CD8+ and FoxP3+ infiltrating cells, and visualization of Granulysin, Perforin, CD137, CD103 and PD-L1 in cervical tissue may be performed. Markers listed here may change as new relevant information becomes available. These tissue response magnitudes will be compared between treatment arms using a difference in means and associated t-distribution based 95% CIs for changes from baseline at each post-baseline time point.

Patient-Reported Outcomes

Subjects enrolled in US, Canada, Mexico, Germany and UK will complete Patient-reported outcome (PRO) questionnaires (SF-36, EQ-5D-5L, and two additional Global PRO questions assessing quality of life after excision or biopsy). Either SF-36 or EQ-5D-5L or both instruments will be completed at baseline, Weeks 4, and Week 12, 8-14 days following each dose, 8-14 days post Week 28, Week 36, 8-14 days post Week 40 and

Week 88. The two additional Global PRO questions assessing quality of life after excision or biopsy will be completed at Week 40.

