For the SF-36, section scores at each of the eight domains (Physical functioning, Role limitations due to physical problems, Bodily pain, General health, Vitality, Social functioning, Role limitations due to emotional problems, and Mental health) and score change from baseline will be summarized at each visit by treatment arm. Scoring of the eight SF-36 subscales will be done by QualityMetric Health Outcomes(tm) Scoring Software 5.0.

For the EQ-5D-5L, each of the five domains (Mobility, Self-care, Usual activity, Pain/discomfort, Anxiety/depression) and Global Health Status Score will be summarized at each visit and relative to baseline by treatment arm.

For the two additional Global PRO questions assessing quality of life after excision or biopsy, the time outcome and the binary outcomes to Y/N question will be summarized by treatment arm.

SF-36 scores will be compared between treatment arms using exact non-parametric 95% confidence intervals for the differences in median changes from baseline. The EQ-5D-5L scores will be analyzed in the same fashion. Days of worsened quality of life for the Week 40 Quality of Life questionnaire will be analyzed using an exact non-parametric 95% confidence interval for the difference in the median number of days. The Y/N worsened quality of life response for the Week 40 Quality of Life questionnaire will be analyzed using a 95% Miettinen and Nurminen confidence interval for the difference in proportions between treatment arms.

In addition, PRO endpoints at each visit that occurs after Week 36 will be summarized according to those with excision (excluding biopsy) versus those without.

The mITT population with at least one post baseline corresponding measurement will be used for PRO analyses.

9. Safety Analysis

All safety summaries and analyses will be based on all subjects in the safety analysis set.

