- f At least 34 mL [4 x 8.5 mL yellow (ACD) tubes] whole blood per time point and 8 mL serum per time point at Screening, Day 0 and Week 8 (4 ml serum per time point at Week 15 and 36). A total of at least 68 mL of whole blood and 16 ml serum should be collected prior to dosing on Day 0.
- g At least 51 mL [6 x 8.5 mL yellow (ACD) tubes] whole blood and 4 mL serum should be collected at Week 15;
- h HPV genotyping and Pap smears are performed on the same ThinPrepTM cervical specimen;
- i Request that the subject abstain from sexual activity and refrain from use of douching or vaginal lubricants/medication for a period of 24 hours prior to cervical specimen collection;
- j Collected prior to the ThinPrepTM sample;
- k A photograph of the lesion with at least one attempt should done as follows: Acetic acid should first be applied to the cervix then photographs of the cervix and the associated lesion should be photographed prior to and after biopsies (if applicable) and at all colposcopic examinations; if repeat photographs are sought, they should be done at the next protocol-specified colposcopy visit.
- 1 Screening colposcopy is optional if adequate colposcopy was performed upon collection of initial biopsy;
- m Screening biopsy of the lesion should be collected as Paraffin-embedded cervical tissue, fresh cervical tissue, or H&E slides. Tissue to be analyzed for evidence of histopathologic regression will be obtained at Week 36 visit either by excision (e.g. LEEP, LLETZ, CKC) or by 4 Quadrant Biopsy or 4 Quadrant Biopsy with ECC based upon the assessment at Week 28 of cytology, HR HPV status, and colposcopic findings (See Tables 4 and 5);

- n Slides from biopsy and/or excised tissue must be reviewed by the PAC and residual cervical tissue from screening and/or Week 36 specimen(s) (paraffin blocks or unstained slides) may be used for immunohistochemistry (IHC) and HPV testing;
- o To be collected only if subject consents for intra-anal sample collection
- p One or both PRO questionnaires (i.e. SF-36 and EQ-5D-5L) will be completed by subjects enrolled in USA, Canada, Mexico, Germany and UK at multiple visits during the study. Additional quality of life questions will be asked at the Week 40 phone call. Refer to Section 6.8 for details
- q Activities at 8 to 14 days Post-Dose 3 phone call may be done at Week 15 if timing overlaps.

PPD Biostatistics and Programming

Statistical Analysis Plan (SAP) Client Approval Form

Client:	Inovio					

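### The durability summary counts anyone HPV-16/18 negative at Weeks 62 and 88, without asking whether she had cleared at Week 36 or has since had an excision

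*SAP*

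**What the plan says.** Exploratory objective 3 (Section 2.3) is to "Describe the durability of virologic clearance of HPV-16 and/or HPV-18 for subjects treated with VGX-3100 compared with those treated with placebo". The matching endpoint (Section 3.2.3, item 3) is "Proportion of subjects with no evidence of HPV-16 and/or HPV-18 by type specific HPV testing at Weeks 62 and 88 visits". Section 8.4 analyses it under the word durability: results are "summarized by number and percentage of subjects with no evidence of HPV-16 and/or HPV-18 by treatment arm at each visit", with windows of Days 420 to 448 for Week 62 and Days 602 to 630 for Week 88.

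Section 8.4 names no population for this summary. The opening of Section 8 supplies the general rule: "All of the efficacy endpoints analyses will use the ITT population".

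Note m to the Schedule of Events (Section 13.1) says Week 36 tissue is obtained "either by excision (e.g. LEEP, LLETZ, CKC) or by 4 Quadrant Biopsy", with or without endocervical curettage, the choice being "based upon the assessment at Week 28 of cytology, HR HPV status, and colposcopic findings". Excision is thus a planned procedure that comes before both durability visits.

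The SAP deals with excision in two other places. Table 1 (Section 8.1) makes a non-responder of a "Subject in which an excision or biopsy sample was obtained between initial dose up to Week 36". For patient-reported outcomes, Section 8.4 states that "PRO endpoints at each visit that occurs after Week 36 will be summarized according to those with excision (excluding biopsy) versus those without". Neither rule reaches the HPV results at Weeks 62 and 88.

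**The concern.** Durability of clearance means staying clear after having cleared. The planned percentage is a cross-section at each late visit and mixes two groups: subjects clear at Week 36 who stayed clear, and subjects not clear at Week 36 who became negative later. The second group says nothing about how long clearance lasts.

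This matters in two ways. Later negativity among non-clearers adds more to the arm with more non-clearers, which is placebo if VGX-3100 works, and so can narrow the contrast. It can also offset relapse among clearers, so that a stable or rising percentage hides loss of clearance.

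**Working it through.** **The plan's own figures.** The SAP gives no figure for the durability analysis. Its only related figure, 90% power with 198 subjects (132 v 66) at 35% v 14% (Section 4.1), reproduces: 90.3% by the pooled normal approximation and 90.8% by exact enumeration of the Miettinen-Nurminen score test at one-sided 0.025. This point does not touch it.

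**Notation.** For each arm:
- p (pV, pP): share clear of HPV-16/18 at Week 36.
- r: share of those clearers still negative at the later visit.
- e: share of Week 36 non-clearers negative at the later visit. If only surgery clears them, e = share excised × share negative after excision.

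**Formulas**, with r and e equal in both arms:
- Planned percentage = p·r + (1 − p)·e, so the planned difference = (pV − pP)(r − e).
- Sustained clearance over all randomised subjects (negative at Week 36 and at the later visit) = p·r, so its difference = r(pV − pP).
- Percentage of Week 36 clearers still negative = r.

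Any e above zero makes the planned difference smaller than the sustained one.

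**Illustration 1: no relapse (r = 1), assumed Week 36 clearance 45% v 25%.** Sustained clearance is 45% v 25%, a difference of 20 points, in every row.

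| Assumed e | Planned display | Difference |
|---|---|---|
| 0 (no later clearance) | 45.0% v 25.0% | 20.0 points |
| 0.60 × 0.50 = 0.30 | 61.5% v 47.5% | 14.0 points |
| 0.80 × 0.90 = 0.72 | 84.6% v 79.0% | 5.6 points |

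Check of the last row: 0.45 + 0.55 × 0.72 = 0.846 and 0.25 + 0.75 × 0.72 = 0.790. Starting from 40% v 20% gives the same differences, since only pV − pP enters.

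**Illustration 2: the SAP's 35% v 14% as a stand-in for Week 36 clearance, r = 0.90.** (Those rates belong to the composite primary endpoint, so this is an assumption.) Sustained clearance is 31.5% v 12.6%, 18.9 points. With 70% of non-clearers excised and half of those negative afterwards, e = 0.35:
- VGX-3100: 0.315 + 0.65 × 0.35 = 0.5425.
- Placebo: 0.126 + 0.86 × 0.35 = 0.427.
- Planned difference: 0.21 × 0.55 = 0.1155, or 11.55 points.
- Share of subjects counted as durable who had not cleared at Week 36: 0.301/0.427 = 70% on placebo and 0.2275/0.5425 = 42% on VGX-3100.

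With e = 0 the planned difference is again 18.9 points.

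**Illustration 3: hidden relapse within one arm.** Take 45% clear at Week 36, 30% of them relapsing, and e = 0.5. The planned percentage is 0.45 × 0.70 + 0.55 × 0.50 = 0.59. The display rises from 45% to 59%, while sustained clearance is 0.45 × 0.70 = 31.5%.

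**If e differs by arm**, the planned difference is r(pV − pP) + (1 − pV)eV − (1 − pP)eP. At 45% v 25% it stays below the sustained difference unless 0.55·eV exceeds 0.75·eP, that is, unless eV is more than about 1.36 times eP.

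**The case against.** The planned summary matches the endpoint as written in Section 3.2.3 and compares randomised groups on HPV status regardless of later surgery. That is a legitimate quantity, and a reader should not call it biased in itself. The shrinkage is relative to sustained clearance, which the SAP does not name as its target. What remains is that the quantity does not answer the stated objective, durability of clearance.

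A reader might infer that the difference will certainly shrink, or shrink by a known amount. The SAP does not support that. It gives neither an excision rate nor a clearance rate after excision, and its Introduction cautions that surgery may leave the HPV infection in place. No shrinkage at all is within the range.

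A reader might also infer that excision will fall mainly on non-clearers and on placebo. The Week 28 criteria make this plausible, but note m refers to selection tables that are not in this document. High-risk HPV also covers more than types 16 and 18, so subjects clear of 16/18 may be excised too.

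The use of all randomised subjects is inferred from the general rule in Section 8, and immunogenicity and PRO analyses do depart from ITT. The inference is reasonable, since nothing in the durability paragraph overrides the rule.

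The PRO split does not prove an inconsistency, because surgery bears directly on quality of life. It shows only that this display is already within the plan's scope. Finally, Section 4.4 has all collected data listed, so it would be too strong to say that durability could never be assessed. What is missing is the planned table that would show it.

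**Conclusion.** The point holds as a mismatch between objective and measure. Followed exactly, Section 8.4 counts subjects who had not cleared at Week 36 as durable and can mask relapse among those who had. This does not depend on surgery, since late spontaneous clearance is miscounted in the same way.

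The numerical effect is an assumption. With no relapse and equal e in both arms, a 20-point difference would appear as anything from 20 points (e = 0) to about 5.6 points (e = 0.72).

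It might be inferred that restricting the table to Week 36 clearers would recover the lost difference. It would not: in Illustration 1 that table reads 100% v 100%. It describes retention, while sustained clearance over all randomised subjects carries the 20-point comparison. Both are needed.

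The stakes are modest. The objective is exploratory and descriptive, with no test, and the primary and secondary results, type I error and power are untouched. The change is still worth making because it is cheap and can be specified in advance.

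**What to change.** In Section 8.4, keep the all-subject percentage and add, by arm and separately for Weeks 62 and 88:

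- (a) Sustained clearance: negative for HPV-16/18 at Week 36 and at the later visit, over all randomised subjects. This keeps the randomised comparison.
- (b) The percentage of Week 36 clearers still negative, labelled descriptive because the subset is formed after randomisation and is small (at an assumed 25% placebo clearance, 0.25 × 66 = about 16 or 17 subjects).
- (c) A split of (a), (b) and the existing percentage by excision v no excision, as already planned for PRO. This split is also post-randomisation and should be read as descriptive.

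Week 36 clearance can follow the virologic responder definition in Table 2, which uses the latest result up to and including the day of first tissue removal. The text should also state the denominator and how a subject with no result in the Week 62 or Week 88 window is counted.

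No new data are needed: the cervical specimen used for genotyping is scheduled at Weeks 36, 62 and 88. The cost is a paragraph of SAP text, a few tables, and thin cells in the split displays.

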4.1. Sample Size

A total of 198 subjects will be randomized to receive either 6 mg VGX-3100 or placebo IM followed by EP in a 2:1 ratio. This sample size provides 90% power to declare VGX-3100 superior to placebo, assuming the true proportion of subjects who achieve the primary endpoints is 35% and 14% for VGX-3100 and placebo, respectively. These proportions also incorporate missing data (~10%) classified as non-regressors (failures). The assumptions are based on the Phase 2 study results.

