4.4. Report Conventions

The following reporting conventions apply generally to tables, listings, and figures:

- Data from all study centers will be combined for analysis;
- P-values will be rounded to 3 decimal places. P-values that round to 0.000 will be presented as '<0.001' and p-values that round to 1.000 will be presented as '>0.999';
- Confidence intervals (Cis) will be presented as 2-sided 95% Cis unless specified differently for a given analysis;
- Summary statistics will consist of the number and percentage of subjects in each category for categorical variables, and the sample size, mean, standard deviation (SD), median, minimum, and maximum for continuous variables;
- Unless otherwise specified, all mean and median values will be formatted to 1 more decimal place than the measured value, standard deviation values will be formatted to 2 more decimal places than the measured value, and minimum and maximum will be formatted to the same decimal place as the measured value;

- All percentages will be rounded to 1 decimal place. The number and percentage of responses will be presented in the form XX (XX.X);
- Unless otherwise specified, all analyses and summary tables will have the analysis population sample size (i.e., number of subjects), and displayed by the treatment arm and total;
- Subjects who received mixed treatments will not be included in the summaries of
 overall safety according to the assigned treatment arm; their data will be reported
 elsewhere.
- All collected data will be listed.
- SAS® Version 9.3 or higher will be the statistical software package used to produce all data summaries, listings, and statistical analyses.

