4.5. Baseline Definition

Baseline is defined as the last measurement prior to the first treatment administration. If the first treatment date is not available, the last measurement before or on the randomization date will be used.

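### Section 8.4 compares tissue immune markers on raw change from baseline without adjusting for the baseline value, which gives up some precision in an exploratory analysis

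*SAP*

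**What the plan says.** For the tissue markers, SAP Section 8.4 prescribes the following analysis: "compared between treatment arms using a difference in means and associated t-distribution based 95% CIs for changes from baseline". It is to be repeated wherever tissue is measured after baseline. The section names no baseline covariate and no model for these markers, and neither does any other section. This is the only between-arm analysis given for exploratory objective 1 (Section 2.3) and exploratory endpoint 1 (Section 3.2.3).

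The work is optional: Section 8.4 says that "visualization of Granulysin, Perforin, CD137, CD103 and PD-L1 in cervical tissue may be performed", and that the marker list may change. Under Section 4.4, intervals "will be presented as 2-sided 95% Cis unless specified differently for a given analysis". No p-value or decision rule is attached to these markers.

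Section 4.5 says: "Baseline is defined as the last measurement prior to the first treatment administration". In the Schedule of Events (Section 13.1), cervical tissue is taken at screening and at Week 36, and footnote n says that "residual cervical tissue from screening and/or Week 36 specimen(s) (paraffin blocks or unstained slides) may be used for immunohistochemistry". CIN grade at screening is a randomization stratification factor (Section 4.2).

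**The concern.** A change score fixes the coefficient on the baseline value at 1. A model with baseline as a covariate estimates that coefficient from the data. When the true within-arm slope is well below 1, as it is when baseline and follow-up are only moderately correlated and equally variable, subtracting the whole baseline value adds noise that the adjusted model removes.

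Every subject who contributes a change has a baseline value, so adjustment loses nobody. What is at stake is the width of the intervals for exploratory objective 1. Because the tissue work depends on residual specimens, paired samples from all 198 subjects look unlikely. That is an inference and not a figure in the SAP.

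**Working it through.** **The plan's own figure.** The SAP states no sample size, power, standard deviation or correlation for the tissue markers. Its only power statement is for the primary endpoint: "This sample size provides 90% power to declare VGX-3100 superior to placebo". With 132 and 66 subjects, 35% against 14% and one-sided 0.025:

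- pooled proportion = (132 × 0.35 + 66 × 0.14)/198 = 0.28
- null SE = sqrt(0.28 × 0.72 × (1/132 + 1/66)) = 0.0677
- alternative SE = sqrt(0.35 × 0.65/132 + 0.14 × 0.86/66) = 0.0596
- power = Φ((0.21 − 1.96 × 0.0677)/0.0596) = Φ(1.30) = 0.903

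Exact enumeration of the Miettinen-Nurminen score test gives 0.908. The stated 90% reproduces, but it has no bearing on the tissue markers.

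**Inputs for this point.** Allocation is 2:1 with 198 subjects (Section 4.1). The baseline to post-baseline correlation ρ, the within-arm standard deviations s0 (baseline) and s1 (post-baseline), and a smaller evaluable number of 60 are assumptions. Slope and variance are taken as common to both arms, and the planned t interval as using a pooled variance.

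**Residual variances.**

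- Change score: s0² + s1² − 2ρ·s0·s1
- Baseline-adjusted model: s1²(1 − ρ²)
- Difference: s0² − 2ρ·s0·s1 + ρ²·s1² = (s0 − ρ·s1)², which is never negative and is zero only when the slope ρ·s1/s0 equals 1

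**Equal standard deviations.** The variance ratio, adjusted to planned, is (1 − ρ²)/(2(1 − ρ)) = (1 + ρ)/2, and the width ratio is its square root. For finite N this is multiplied by t(0.975, N−3)/t(0.975, N−2) × sqrt(1 + 1/(N−4)), which covers the lost degree of freedom and the expected chance imbalance.

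| ρ | variance ratio | width ratio | planned interval wider by | width ratio, N = 198 | width ratio, N = 60 |
|---|---|---|---|---|---|
| 0.3 | 0.65 | 0.806 | 24% | 0.81 | 0.81 |
| 0.5 | 0.75 | 0.866 | 15% | 0.87 | 0.87 |
| 0.7 | 0.85 | 0.922 | 8% | 0.92 | 0.93 |
| 0.9 | 0.95 | 0.975 | 3% | 0.98 | 0.98 |

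The fourth column uses the ratio without the finite-N factor. With that factor at N = 198 the excess widths are 24%, 15%, 8% and 2%.

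**Simulation** (2,000 runs per setting, normal data, equal standard deviations). Mean width ratios at ρ = 0.3, 0.5 and 0.7 were 0.81, 0.87 and 0.92 at N = 198, with the adjusted interval narrower in every run. At N = 60 they were 0.81, 0.87 and 0.93, with the adjusted interval narrower in 94% to 99.95% of runs.

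**Unequal standard deviations** (width ratio without the finite-N factor). With s1/s0 = 0.75 the ratios at ρ = 0.3, 0.5 and 0.7 are 0.68, 0.72 and 0.75, so the gain is larger. With s1/s0 = 1.5 they are 0.93, 0.98 and 1.00. With s1/s0 = 2 and ρ = 0.5 the slope is exactly 1 and there is no gain.

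**Worst case for adjustment.** With the slope at 1, the finite-N factor alone makes the adjusted interval wider by 0.3% at N = 198, 0.9% at N = 60 and 2.1% at N = 30.

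**The case against.** The strongest reply is that nothing here is wrong. A t interval on change is a valid, familiar analysis, unbiased under randomization, and the SAP uses change from baseline elsewhere: for ELISpot and flow cytometry (Section 8.3) and for the SF-36 and EQ-5D-5L (Section 8.4). The assessments are optional and no conclusion rests on them. The correlation is unknown, so the loss could be trivial. Equal standard deviations are not supported either: baseline tissue is a screening lesion biopsy, while Week 36 tissue is an excision or a four-quadrant biopsy (Section 13.1, footnote m). Section 11 does not list this analysis as a change, so it presumably follows the protocol.

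Most of this stands, and it sets the priority. It does not remove the point. The variance inequality needs no equal standard deviations; only the percentages do. The immunogenicity and quality-of-life comparisons use differences in medians with exact non-parametric intervals, to which this argument does not carry over directly. The tissue comparison uses means, where a covariate enters simply. One caveat is fair: if slopes differ by arm under 2:1 allocation, the ordering is not guaranteed for a common-slope model.

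Three stronger readings should be resisted:

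- **Bias.** A reader might infer that chance baseline imbalance or regression to the mean biases the estimate. Under randomization both average to zero between arms, and their variation is already in the change-score variance. It is the same loss of precision, not a second fault.
- **Power.** A reader might turn the variance ratio into a loss of power. The SAP plans no test of these markers, so interval width is the relevant measure.
- **Missing tissue.** The proviso about sample availability in Section 3.2.3 attaches to the additional markers, not to CD8+ and FoxP3+, so it does not show that those two will be short of tissue.

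**Conclusion.** The point holds as a low-priority improvement in precision. Given a common within-arm slope and variance, the planned interval is wider than a baseline-adjusted one unless the slope is near 1. With equal standard deviations the excess is about 24%, 15%, 8% and 3% at ρ = 0.3, 0.5, 0.7 and 0.9. Where the true figure lies cannot be settled from the SAP, which gives neither the correlation nor the standard deviations. The planned comparison remains valid, and no primary, secondary or safety conclusion depends on it.

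**What to change.** In Section 8.4, replace the t interval on change scores with a linear model of the post-baseline marker value (or, equivalently for the arm effect, the change) on treatment arm and the baseline marker value. CIN grade may be added because it is a stratification factor. Report the adjusted arm difference with its t-based 95% CI at each post-baseline time point.

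If a log scale is wanted, fix it in advance for each marker with a rule for zero values, and report a ratio. A transformation chosen after seeing the data would leave the estimand open. List the change in Section 11 if it departs from the protocol.

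The cost is a sentence or two and a standard model, with no new data. The downside is one degree of freedom per covariate: with baseline alone, about 1% to 2% more width in a small sample if the slope is near 1.
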